3.5 CONCOMITANT MEDICATIONS

Concomitant medications taken within 30 days of screening through 30 days following discontinuation of study treatment need to be recorded in the source documents.

The following medications are prohibited from 28 days prior to the Day 0 visit through the end of treatment:

- Hematologic stimulating agents (e.g., erythropoiesis-stimulating agents (ESAs); granulocyte colony stimulating factor (GCSF); thrombopoietin (TPO) mimetics)
- Chronic systemic immunosuppressants including, but not limited to, corticosteroids (prednisone equivalent of >10 mg/day for >2 weeks), azathioprine, or monoclonal antibodies (e.g., infliximab)
- Investigational agents or devices for any indication
- Concomitant use of certain medications or herbal/natural supplements (inhibitors or inducers of drug transporters i.e., P-gp) with study drug(s) may result in pharmacokinetic interactions resulting in increases or decreases in exposure of study drug(s). Examples of representative medications which are prohibited from 21 days prior to Day 0 through the end of treatment are listed below.
- Medications for disease conditions excluded from the protocol (e.g., active cancer, transplantation) are not listed under this Concomitant Medication section and are disallowed in the study.

• Should subjects have a need to initiate treatment with any disallowed concomitant medication, the medical monitor must be consulted prior to initiation of the new medication

Drug Class	Agents Disallowed	Use with Caution
Acid Reducing Agents ^a		Proton-Pump Inhibitors, H2-Receptor Antagonists, Antacids
Anticoagulants		Dabigatran Etexilate ^d
Anticonvulsants ^b	Phenobarbital, Phenytoin, Carbamazepine, Oxcarbazepine	
Antimycobacterials ^b	Rifabutin, Rifapentine, Rifampicin	
Cardiac Medications	Amiodarone ^c	Digoxin ^d
Herbal/Natural Supplements ^b	St. John's Wort, Echinacea, Milk thistle (i.e., silymarin), Chinese herb sho-saiko-to (or Xiao-Shai-Hu-Tang)	
HMG-CoA Reductase Inhibitors ^e	Rosuvastatin	Pravastatin

Table 3-1: Disallowed and Concomitant Medications to be Used with Caution

a Proton-pump inhibitors (PPIs) comparable to omeprazole 20 mg once-daily may be taken. H2 receptor antagonists must not exceed the equivalent of 40 mg of famotidine twice daily. Antacids that directly neutralize stomach pH (i.e. Tums, Maalox) may not be taken within 4 hours (before or after) of SOF/VEL/VOX FDC administration.

b May result in a decrease in the concentrations of study drugs.

c May result in symptomatic bradycardia. Mechanism is not currently known. The use of amiodarone is prohibited from **60 days prior to Day-1** through the end of treatment.

d May result in an increase in the concentration of study drugs and/or concomitant medications

e Use with study drugs may result in an increase in the concentration of the HMG-CoA Reductase Inhibitors. Monitor for signs and symptoms of muscle weakness or myopathy, including rhabdomyolysis. Pravastatin may be administered with SOF/VEL/VOX FDC at a dose that does not exceed pravastatin 40 mg.

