- 4. Poorly controlled diabetes as indicated by a screening glycosylated hemoglobin (HbA1c) >10
- 5. Known hypersensitivity to any of the study medications
- 6. Screening ECG with clinically significant findings
- 7. Need for the use of the following medications from 21 days prior to the start of study drugs through the end of treatment:
 - a. Hematologic stimulating agents, erythropoiesis stimulating agents (ESAs), granulocyte colony stimulating factor (GCSF), thrombopoeitin (TPO) mimetics
 - b. Chronic systemic antineoplastic or immunomodulatory treatment including supraphysiologic doses of immunosuppressants such as corticosteroids (e.g., prednisone equivalent >10 mg/day for >2 weeks), azathioprine or monoclonal antibodies (e.g., infliximab)
 - c. Investigational agents or devices for any indication
 - d. Use of certain medications and herbal/natural supplements per PI discretion, expected to result in increases or decreases in exposure to study or non-study medications as listed in section 3.5 (Table 3-1).
- 8. Any medical, psychiatric, social condition, occupational reason or other responsibility that, in the judgment of the investigator, is a contraindication to protocol participation or impairs a volunteer's ability to give informed consent.

Female-specific criteria:

9. Woman who is breast-feeding or planning to become pregnant during the first 24 weeks after study drug administration.

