Each patient will provide informed consent of his/her free will prior to commencement of any study procedures according to ICH and Code of Federal Regulations (CFR). Each patient will be provided a copy of the signed informed consent form.

After a patient has provided informed consent, the Investigator and other study personnel will determine if the patient is eligible for participation in the study. Screening may begin up to 8 weeks prior to dosing to allow for a possible liver biopsy if one has not been performed within 36 months prior to the first dose of study drug (Day 0) and is indicated for disease staging as specified in the inclusion criteria. An optional research liver biopsy will be offered to subjects during screening (and at end of treatment) with the aim of having paired research samples on up to 20 subjects on the study.

Screening will include a review of the inclusion/exclusion criteria and completion of all screening procedures as outlined in the Schedule of Tests, Section 5.1. Screening tests within the last 8 weeks prior to screening visit that have been done as part of routine medical care or at an outside facility (with the exception of chemistries, hCG, HIV, CBC with differential, coagulation studies) can be used if within the acceptable time frame. Known HIV infected participants will not have an HIV test, but will have HIV RNA and CD4 T-Cell count testing.

The standard consent includes permission for HIV testing (in those not previously known to be infected), optional liver biopsy, and storage of blood and tissue samples. HLA testing may be tested for this study if not on file, because this information will be useful for the evaluation of HCV-specific immune responses.

Screening procedures do not need to be repeated within the 8 week screening window unless clinically indicated. Once the screening window has elapsed, patients may be rescreened at the discretion of the PI.

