2.10 HISTORY AND PHYSICAL

All subjects will have a History and Physical during the screening process as part of final determination of protocol eligibility. Physical exams will be performed with study point visits at Day 0, Week 4, Week 12 and Post-treatment Weeks 12 and 24. Directed physical exam will be done as needed at other study points. On arrival at the clinic for study visits, subjects will have their vital signs obtained and females of childbearing potential will undergo a pregnancy test (if appropriate per visit day, see Schedule of Tests, Section 5.1), clinical laboratories drawn, and a review of the study restrictions. Subjects will be asked about their state of health and use of any concomitant medication since the previous study visit. They will also be questioned about AEs, their adherence with study restrictions, and their adherence to study drug administration. A complete list of study procedures and lab tests to be performed is in the Schedule of Tests, Section 5.1.

In addition, subjects may be seen at unscheduled visits for a grade 3 or 4 AE or any unexpected AE (adverse event) or potential toxicity.

Some of the visits have flexibility regarding when they need to occur. The window period for visit schedules is as follows:

- Days 0, 3(PK/VK participants only), no window
- Optional Week 1 (+/- 3 days)
- Weeks 2, 4 (+/- 3 days)
- Weeks 8 and 12 (+/- 7 days)
 - Optional End of therapy Liver Biopsy (+/-14 days)
- Post Therapy Weeks 4, 12, 24 (+/- 10 days)

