3.3 TREATMENT OF SUBJECTS

All subjects will receive 12 weeks of treatment with SOF/VEL/VOX.

SOF/VEL/VOX FDC will be administered orally once a day. The 1st dose will be taken on Day 0.

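### Look-back windows for amiodarone conflict (21, 28 and 60 days), and the medication record in section 3.5 need not reach the start of the longest one

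*Combined protocol and SAP*

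**What the plan says.** Four places in the protocol bear on prior amiodarone use.

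- **Exclusion criterion 7 (section 2.4.2)** opens with "Need for the use of the following medications from 21 days prior to the start of study drugs through the end of treatment". Item 7d under it points to the agents in Table 3-1, which include amiodarone.
- **Section 3.5, list of prohibited medications.** The list is headed with a period of 28 days before Day 0. The bullet within it that introduces Table 3-1 gives another: "Examples of representative medications which are prohibited from 21 days prior to Day 0 through the end of treatment are listed below".
- **Table 3-1, footnote c** sets a period for this drug alone, with possible symptomatic bradycardia as the reason: "The use of amiodarone is prohibited from 60 days prior to Day-1 through the end of treatment".
- **Section 3.5, opening sentence** sets what must be written down: "Concomitant medications taken within 30 days of screening through 30 days following discontinuation of study treatment need to be recorded in the source documents".

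Two further statements fix the calendar. On dosing, section 3.3 says "The 1st dose will be taken on Day 0". On screening, section 2.8.1 says "Screening may begin up to 8 weeks prior to dosing". No minimum interval between screening and dosing is given.

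**The concern.** There are two linked problems.

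First, the rules that decide who may be dosed do not agree. A site that works from exclusion 7 or from the table's lead-in looks back 21 days. A site that works from footnote c looks back about 60. The text does not say which governs, and exclusion 7 does not mention the longer period.

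Second, the required record is counted back from screening, whereas every prohibition is counted back from dosing. When screening is close to dosing, the record stops short of the start of the footnote c window.

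At stake is whether the trial can show that it kept its own rule. Safety and tolerability are part of the primary objective, and footnote c is the only entry in Table 3-1 with its own longer period. If earlier use is neither asked about nor written down, a deviation may not be noticed. A later bradycardia event might then be assessed for causality without a relevant exposure on file. The sample size and the SVR12 analysis are not affected.

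**Working it through.** The plan states no figure for this gap, so there is none to reproduce. The check is calendar arithmetic.

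**Inputs**
- First dose: Day 0 (section 3.3).
- Screening: s days before Day 0, with s from 0 to 56 (8 weeks, section 2.8.1).
- Start of the required record: 30 days before screening, that is s + 30 days before Day 0 (section 3.5).
- Start of the amiodarone prohibition: 60 days before Day -1, that is 60 + 1 = 61 days before Day 0 (footnote c).
- Exclusion 7 and the Table 3-1 lead-in: 21 days before Day 0. Heading of the list in section 3.5: 28 days.

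**Step 1: conflict between the rules.** Footnote c reaches 61 - 21 = 40 days further back than exclusion 7 and the lead-in, and 61 - 28 = 33 days further than the heading of the list. This does not depend on when the subject is screened.

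**Step 2: prohibited days outside the required record.**

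Gap = max(0, 61 - (s + 30)) = max(0, 31 - s)

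| s (days from screening to Day 0) | Record starts (days before Day 0) | Prohibited days not required to be recorded |
|---|---|---|
| 0 | 30 | 31 |
| 7 | 37 | 24 |
| 14 | 44 | 17 |
| 21 | 51 | 10 |
| 28 | 58 | 3 |
| 31 | 61 | 0 |
| 56 | 86 | 0 |

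**Step 3: sensitivity to the meaning of Day -1.** If the day of first dose was meant, the prohibition starts 60 days before Day 0 and the gap closes from s = 30. If the day after Day 0 was meant, it starts 59 days before and the gap closes from s = 29. At s = 7 the gap is 24, 23 or 22 days under the three readings. The finding survives each.

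**Step 4: an example.** A subject stops amiodarone 45 days before Day 0 and is screened 10 days before Day 0. The required record reaches back 10 + 30 = 40 days, so the use at 45 days lies outside it. It also lies outside the 21-day and 28-day periods, but inside the 61 days of footnote c.

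**Step 5: does another section supply the record?** At study visits subjects are asked about "use of any concomitant medication since the previous study visit" (section 2.10), which adds no look-back. The text of section 5.1 lists no medication-history item. No eligibility criterion states the 60-day period.

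**The case against.** The strongest reply is that footnote c already governs. Item 7d sends the reader to Table 3-1, and a footnote written for one drug would ordinarily qualify the general lead-in. On that reading the subject in the example may not be dosed, and the recording sentence is beside the point: it sets what must be recorded and does not limit what may be asked. Screening includes an eligibility review and a history and physical. Source documents include hospital and office records, and every subject must have a primary care doctor. Exclusions 2f (significant cardiac disease), 6 (clinically significant screening ECG findings) and 8 (investigator judgment) narrow the group further.

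Much of this stands, and it rules out several stronger conclusions that a reader might draw:

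- *That the example subject is eligible.* Item 7d leads to the table that carries footnote c, so the documents leave this unresolved.
- *That the trial cannot enforce its rule, or will hold no trace of the exposure.* One screening question would enforce it, and outside records may show the use. What is established is only that section 3.5 does not require the record.
- *That a safety event follows.* Footnote c speaks of a possible effect. The direct consequence is an unverified or undocumented deviation.

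What the reply does not remove is the conflict itself. Exclusion 7 states 21 days with no exception. Its stem concerns a need for the drug, which fits poorly someone who stopped weeks earlier. Item 7d is left to the investigator's discretion and concerns agents that alter drug exposure, whereas footnote c gives bradycardia of unknown mechanism as its reason. It is therefore unclear whether 7d reaches amiodarone at all. And a history that might ask is not a required check.

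**Conclusion.** The point holds as an inconsistency between stated rules, joined to a recording window that can be too short to verify the longest of them. The eligibility and prohibition windows differ by up to 40 days for every subject. The recording shortfall is 31 - s days for subjects screened fewer than 31 days before dosing, at most 31 days, and nil for those screened 31 to 56 days before.

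This rests on three assumptions: the 30-day recording period is counted back from screening, Day -1 is the day before Day 0 (other readings move the threshold by one or two days), and screening may fall close to dosing because no minimum interval is stated.

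The number of subjects affected cannot be derived. The documents give neither the distribution of screening intervals nor the frequency of amiodarone use. It is likely to be small and may be zero. The correction is still worth making because it is cheap and concerns a safety prohibition.

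**What to change.** 1. **Reconcile the windows.** Bring exclusion 7, the 28-day and 21-day statements in section 3.5, and footnote c into agreement, so that eligibility and prohibition use one window per drug. If a drug is to keep its own window, state it in exclusion 7 as well as in the footnote. Which window is kept is for the sponsor. The same edit should settle the hematologic stimulating agents, immunosuppressants and investigational agents, which carry 21 days in exclusion 7 and 28 days in section 3.5.
2. **Re-anchor the record.** In section 3.5, count the recording look-back for Table 3-1 agents from Day 0 and make it at least as long as the longest prohibition window retained. If footnote c stays as written, the record must start 61 days before Day 0 whatever the screening date.
3. **Clarify the day count.** Say what Day -1 means in a protocol where dosing starts on Day 0.

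The cost is a few sentences and a slightly longer medication history at screening. No visit, test or analysis changes.

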4 STATISTICAL CONSIDERATIONS

This study is a single-center trial to assess the safety and tolerability of SOF/VEL/VOX.

4.1 SAMPLE SIZE

We anticipate enrolling approximately 60 patients with cirrhosis and 60 patients without cirrhosis, for a total of 120 HCV, genotype 1, infected subjects who have previously been treated with unsuccessful combination DAA-based therapy.

An anticipated sample size of approximately 120 patients will provide a 97% power to detect at least an absolute 15% improvement in SVR_{12} from the conservative estimate of 70%²⁰ by using a 2-sided, exact, 1-sample binomial test at a significant level of 0.05 (See Table 4-1).

H _o SVR12	H _a SVR12	Sample Size	Power
70%	80%	120	0.641
70%	85%	120	0.968
70%	90%	120	>0.999
70%	95%	120	>0.999

In terms of safety, a sample size of 120 is sufficient to have high probability of observing at least 1 adverse event of probability 5% or more. If the true event probability is 5% or more, there is about a 99.8% chance of observing at least 1 such adverse event. Consequently, if no one has a given type of AE, we can be confident that its true probability is under 5%. This trial will provide preliminary evidence on the safety and efficacy of SOF/VEL/VOX. A previous study of SOF/VEL FDC in subjects with genotype 1 led to a sustained virologic response at Week 12 (SVR₁₂) in all participants. We therefore expect SVR to 80% or higher. If the true suppression rate is 80%, we will be able to estimate the probability of suppression to within approximately $\pm 1.96[(.8)(1-.8)/120]^{1/2}=.07$ (Table 4-2). For sample sizes shown in row 1, row 2 gives the accuracies of the estimates of the proportion of patients suppressed to below the limit of detection (based on a 95% confidence interval).

Table 4-2: Sample Size

n=50	n=75	n=100	n=120
±.11	±.09	$\pm.08$	±.07

AE probabilities are shown in Table 4-3, wherein for a given N, the probability of observing at least 1 participant with the AE among study participants. We selected at least 100 participants based on the ability to detect adverse event rates of a frequency of 1% and 5% with 63% and 99% probability, respectively.

Table 4-3: Adverse Event Probability Table

	Probability of Adverse Event				
	0.01	0.05	0.10	0.15	
N=75	52%	98%	>99.9%	>99.9%	
N=100	63%	99%	>99.9%	>99.9%	
N=120	70%	99.8	>99.9%	>99.9%	

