1.2 RATIONALE FOR NEW COMBINATION DAA THERAPIES

Despite the high efficacy of currently approved combination DAA therapies, some patients do not successfully clear HCV, either due to non-adherence, viral resistance, virologic breakthrough, or virologic relapse. The ideal strategy for pursing HCV clearance in these patients remains uncertain, and careful clinical trials assessing the safety and efficacy of retreatment strategies in these patients need to be conducted. While some groups have demonstrated high response rates (>90%) after previous failure of a short course regimen¹⁹, despite the presence of resistance associated HCV variants (RAVs), others have reported low treatment response rates, in some cases less than 50%, related to treatment emergent NS5A RAVs²⁰. In these small studies, it is unclear whether viral, treatment or host factors drive the low response rates. This study seeks to address this question and determine whether a universal "salvage" regimen would be safe, tolerable, and effective in patients failing a diverse array of combination DAA-based therapies.

Sofosbuvir, a nucleotide analogue chain terminating inhibitor of the NS5B HCV viral polymerase, was approved by the FDA in December 2013, and of note, treatment emergent resistance to NS5B inhibitors has not been observed in patients failing SOF-based regimens²¹. The investigational agents Velpatasvir (VEL, formerly GS-5816) which inhibits the NS5A protein, and Voxilapravir, the NS3/4 viral protease, have shown promise in early clinical studies²²⁻²⁴, including efficacy of approximately 90% in patients who had previously failed

combination DAA-based therapy^{25, 30,31}. In patients who have previously failed combination DAA therapy, including LDV/SOF, paritaprevir/ritonavir/ombitasvir/dasabuvir (PrOD), and elbasvir/grazoprevir (EBR/GZR)-based combination DAA regimens, we hypothesize that retreatment with at least two novel drugs will be safe and effective, overcoming baseline or treatment emergent viral resistance and inhibiting viral replication.

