1.6 SOF/VEL/VOX

1.6.1 Voxilaprevir

Voxilaprevir (Gilead product no. GS-9857) is a novel macrocyclic HCV NS3 protease inhibitor with potent in vitro antiviral activity against genotypes 1 to 6 HCV, broad coverage of NS3 protease polymorphs, and an improved resistance profile compared with PIs approved by the Food and Drug Administration (FDA) or currently in clinical development. Please refer to the IB for SOF/VEL/VOX for additional information on Voxilaprevir including:

- In Vitro Anti-Hepatitis C Virus Activity
- Nonclinical PK and In Vitro Metabolism
- Nonclinical Pharmacology and Toxicology
- Clinical Experience

1.6.2 Summary of Clinical Experience with SOF/VEL/VOX

Data from three Phase 2 studies, GS-US-337-1468 (LEPTON), GS-US-367-1168, and GS-US-367-1169, support the efficacy of 12 week therapy with SOF/VEL/VOX in subjects with DAA experience. In the LEPTON study, 67% (20/30) subjects who had previously failed 2 DAAs and then received 6 weeks of SOF/VEL+VOX achieved SVR12. In Study GS-US-367-1168, 100% (63/63) genotype 1 subjects that had previously failed DAAs and received 12 weeks of SOF/VEL+VOX achieved SVR12. In Study GS-US-367-1168, 100% (63/63) genotype 2-6 HCV who were treatment experienced, including 38 subjects who had failed a DAA, and received 12 weeks of SOF/VEL+VOX achieved SVR12. Treatment was safe and generally well tolerated. No safety signal associated with the administration of these agents was identified.

1.6.3 FDA-approval

The fixed dose combination with SOF/VEL/VOX was approved in the U.S. by the FDA on 17 July 2017 and is indicated for the treatment of adult patients with chronic HCV infection without cirrhosis or with compensated cirrhosis (Child-Pugh A) who have:

• genotype 1, 2, 3, 4, 5, or 6 infection and have previously been treated with an HCV regimen containing an NS5A inhibitor.

• genotype 1a or 3 infection and have previously been treated with an HCV regimen containing sofosbuvir without an NS5A inhibitor.

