4.1.1 Primary Endpoint

The primary efficacy endpoint is SVR₁₂ (HCV RNA <LLOQ 12 weeks after cessation of therapy).

The primary statistical hypothesis for efficacy is that SVR_{12} rate is higher than the conservative estimate of $70\%^{20}$.

- $H_0: SVR12 = 70\%$
- $H_a: SVR12 \neq 70\%$

The primary analysis will be intention-to-treat, including all enrolled subjects into the study and received at least one dose of study drug, performed after all enrolled subjects have been followed through 12 weeks post-treatment or discontinued from study.

4.1.2 Secondary Endpoints

Secondary efficacy endpoints include: HCV RNA < LLOQ at 4 and 24 weeks after discontinuation of therapy (SVR₄ and SVR₂₄); viral breakthrough; and relapse.

Descriptive summaries and listings will be provided for additional efficacy evaluations of the proportion of subjects who experience virologic failure and other endpoints of interest including ALT normalization, serum HCV RNA actual values, and change from baseline.

Exploratory analyses may be performed to assess the relationship between demographic, baseline characteristics, (including baseline viral load, genotype, age, sex, race, ethnicity, presence/absence of cirrhosis, baseline ALT level, prior treatment experience, response to previous treatment [if applicable], and BMI) and antiviral activity (HCV RNA reduction, proportion of subjects with HCV RNA <LLOQ at various time points during and following discontinuation of all therapy). Predictive factors of antiviral activities may be examined using regression type of analysis. Changes in HCV specific CD8 responses in patients with cirrhosis and not with cirrhosis. Changes in HCV specific immune responses in patients treated with single (NS5B) DAA versus dual (NS5B + NS5A) versus triple combination DAA (NS5B + NS5A + NS3) using samples from SPARE and this study

4.1.3 Safety Endpoints

The primary safety endpoint is any AE leading to permanent discontinuation of study drug(s).

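### Does Section 4.1 need to name an exact confidence interval and p-value construction because its only interval formula is a normal approximation?

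*Combined protocol and SAP*

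**What the plan says.** Section 4.1 tests SVR12 against 70% with about 120 patients "by using a 2-sided, exact, 1-sample binomial test at a significant level of 0.05". The same sentence points to Table 4-1, which prints power 0.641 at a true 80% and 0.968 at 85%.

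Later in the section the plan turns to precision. It says "We therefore expect SVR to 80% or higher", then: "If the true suppression rate is 80%, we will be able to estimate the probability of suppression to within approximately" 0.07, from 1.96 times the square root of (0.8)(0.2)/120. Table 4-2 applies the formula to n = 50, 75, 100 and 120 and describes the result as the accuracy of estimating "the proportion of patients suppressed to below the limit of detection (based on a 95% confidence interval").

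Section 4.1.1 gives the null, the two-sided alternative, the timing and the analysis set: "The primary analysis will be intention-to-treat, including all enrolled subjects into the study and received at least one dose of study drug". Neither it nor the rest of Section 4 names an interval method for the observed SVR12 or says how the two-sided exact p-value is built. On group sizes, Section 4.1 says: "We anticipate enrolling approximately 60 patients with cirrhosis and 60 patients without cirrhosis".

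**The concern.** Read quickly, Section 4.1 pairs an exact test with a normal-approximation interval. Two things could then go wrong.

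First, the interval and the test could disagree about 70%, because the approximate interval excludes 70% at counts where the exact test does not reject. The phrase two-sided exact is also not unique. One can double the smaller tail, or sum the probabilities of all outcomes no more likely than the one observed (minimum likelihood). If these differ at the observed count, a software default decides the primary result.

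Second, the ±1.96 interval behaves badly near 100%, which is where much of the protocol's evidence lies. Section 1.2 speaks of "including efficacy of approximately 90% in patients who had previously failed" combination DAA therapy, Section 1.6.2 reports "100% (63/63) genotype 1 subjects that had previously failed DAAs and received 12 weeks of SOF/VEL+VOX achieved SVR12", and Section 1.6.4 cites 95-97%. At such rates rejection of 70% is nearly certain, so the interval is the informative result. One that is too narrow, passes 100% or has zero width would overstate efficacy, and more so in cirrhosis groups of about 60.

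**Working it through.** **Inputs.** n = 120, null 70%, two-sided 0.05, power 0.641 and 0.968, half-width 0.07 (all Section 4.1 with Tables 4-1 and 4-2); cited efficacy 95-97% (Section 1.6.4).

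**1. Reproduce the plan's figures.** X is the number of responders, X ~ Bin(120, p). Doubling the smaller tail at p = 0.70:
- P(X ≥ 94) = 0.0266, doubled 0.053: not rejected.
- P(X ≥ 95) = 0.0159, doubled 0.032: rejected.
- P(X ≤ 73) = 0.0200, doubled 0.040: rejected.

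The rule therefore rejects at 95 or more, or 73 or fewer. P(X ≥ 95) is 0.641 at p = 0.80 and 0.968 at p = 0.85, with a negligible lower-tail contribution. Both match Table 4-1.

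Half-widths 1.96·√(0.16/n) are 0.111, 0.091, 0.078 and 0.072 for n = 50, 75, 100 and 120. These match Table 4-2.

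**2. Which exact rule does Table 4-1 use?**

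| Upper cut-off | Rule | Power at 80% | Power at 85% |
|---|---|---|---|
| 93 | ±1.96 interval excludes 70% | 0.790 | 0.990 |
| 94 | exact, minimum likelihood | 0.721 | 0.981 |
| 95 | exact, doubled tail | 0.641 | 0.968 |

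Of these, only the cut-off of 95 gives the printed figures.

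**3. Where the readings differ.** The approximate interval is p̂ ± 1.96·√(p̂(1−p̂)/120). The Clopper-Pearson limits are the 2.5% quantile of Beta(x, 121−x) and the 97.5% quantile of Beta(x+1, 120−x).

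| Count | ±1.96 interval | Clopper-Pearson | p, doubled tail | p, min. likelihood |
|---|---|---|---|---|
| 93 | 70.03-84.97% | 68.98-84.62% | 0.085 | 0.074 |
| 94 | 70.96-85.70% | 69.89-85.33% | 0.053 | 0.047 |
| 95 | 71.90-86.43% | 70.80-86.04% | 0.032 | 0.028 |

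At 93 the two exact tests agree, and only the approximate interval stands apart. The exact tests split only at 94. P(X = 94) is 8.0% at a true 80%, 1.3% at 85% and 0.008% at 90%. Counting 93 as well gives 14.9%, 2.2% and 0.01%.

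The split also depends on n. For n = 110 to 130 the two exact upper cut-offs coincide at 18 of 21 sizes and differ only at 113, 120 and 124. At the accrual ceiling of 150 both are 117. The plan says approximately 120.

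**4. Coverage if the ±1.96 formula were used for reporting.** Exact binomial sums give:
- n = 120: 94.3% at a true 80%, and a mean of 93.8% over 80-90%.
- n = 120 over 95-97%: mean 90.7%, minimum 85.0%.
- n = 60 over 95-97%: mean 89.7%, minimum 79.8%.
- n = 120 at 97%: the interval lies wholly above the truth in 12.2% of trials and wholly below it in 0.3%.
- 60/60 gives 100-100%, where Clopper-Pearson gives 94.0-100%. Its probability at a true 97% is 0.97^60 = 16.1%.

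Clopper-Pearson coverage over 95-97% is at least 95.3% (n = 120) and 97.5% (n = 60).

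**5. Does the plan call for that use?** The formula is introduced by a condition (a true rate of 80%), sits under the sample-size heading and feeds a table of sample sizes. Sections 4.1.1 to 4.4 do not refer back to it. No SVR12 interval by cirrhosis status is specified. In the Study Summary, the secondary comparison by disease stage concerns end-of-treatment response, SVR4 and SVR24. Sections 2.3 and 4.1.2 treat the effect of cirrhosis on response as exploratory.

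**The case for a change.** The strongest case for acting is that the omission is real and cheap to close. No analysis interval is named for the primary efficacy estimate, and the only formula on the page is unsuitable at the rates the protocol itself cites. At 94/120 the choice of algorithm moves p across 0.05. At a true 80%, the floor of the expected range, the chance of a count where some reading disagrees is 14.9%. The primary objective covers patients with and without cirrhosis, so intervals at n of about 60 may well be reported. One sentence would settle all of this without touching N, alpha or power.

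The arithmetic stands in full, and so does the advice not to use the ±1.96 formula for rates near 100%. The step from planning formula to reporting formula does not stand, because the plan never takes it. More than half of the risk argument about 93 and 94 weakens accordingly: at 93 only that unplanned interval dissents, and at 94 Table 4-1 already shows which exact rule the sponsor computed. The two harms also do not occur together. Disagreement at 93-94 needs a true rate near 80%, where the formula covers about 94%. Undercoverage needs 95-97%, where, at 95% for example, 93 or 94 of 120 has probability about 2 in 10 billion. Finally, intervals by cirrhosis status would be an addition to the plan, not a clarification of it.

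**Conclusion.** No change follows. The conflict between test and interval, and the undercoverage, belong to an analysis the plan does not describe. Followed as written, the exact test is sound, and Tables 4-1 and 4-2 reproduce in the entries checked. The undefined p-value is resolved by Table 4-1, which fits only the equal-tailed rule that rejects from 95/120. What is left is a missing detail, the interval method for the observed SVR12. An analyst running an equal-tailed exact test would ordinarily report the Clopper-Pearson interval, which agrees with that test at every count.

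The residual exposure is a single count, 94 of exactly 120, with probability 8.0% at a true 80%, 1.3% at 85% and 0.008% at 90%. It arises only if the analyst departs from the rule behind Table 4-1. This conclusion rests on two assumptions: that the ±1.96 expression is planning precision only, as its wording and placement indicate, and that the analyst keeps to the rule used for the power table.
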